	Part 1B is planned to start before the MTD/RP2D is reached in Part 1A using a bifurcated trial design. The dose level of BNT411 in Part 1B at any given time will always be one dose level below that in Part 1A.
	In Parts 1A and 1B, patients will receive one infusion of BNT411 every week in a 3-week cycle for the first 4 cycles (on Days 1, 8 and 15 in Part 1A; on Days 2, 8 and 15 in Part 1B). In the following cycles thereafter, BNT411 will be administered every 3 weeks (on Day 1 [Part 1A] or Day 2 [Part 1B] of each 3-week cycle). Treatment will continue until protocol-defined treatment discontinuation criteria are met.
	The dose escalation in Part 1A starts with an accelerated phase consisting of single patient cohorts followed by larger patient cohorts in Parts 1A and 1B informed by a classical 3+3 design. BNT411 dosing in Part 1A will start at 0.05 µg/kg/administration.
	To be eligible for DLT assessment, patients should receive all three infusions of BNT411 during the DLT assessment period (Cycle 1). After completion of the DLT period, the Safety Review Committee (SRC) will review the data and propose the dose level for the next cohort of patients. The RP2D will be decided based on integrated evaluation of safety, tolerability, clinical benefit, PK, and pharmacodynamic data, for all dose levels tested.
	Efficacy will be assessed by on-treatment imaging at Week 6 (+7 days), every 6 weeks (±7 days) for 48 weeks, and every 12 weeks (±7 days) thereafter until disease progression is assessed by the investigator (unless the investigator elects to continue treatment), withdrawal of consent, trial termination by the sponsor, or death, whichever occurs first, regardless of whether patients start a new anti-cancer therapy.
Population	Between 6 to 60 DLT evaluable patients are planned to be enrolled in Part 1A. Between 6 to 30 DLT evaluable patients are planned to be enrolled in Part 1B.

For the dose escalation (Parts 1A and 1B), approximately 12 sites will be opened in North America and Europe. For possible expansion, approximately 25 to 35 sites will be opened in North America, Europe, and potentially the rest of the World.

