# 4 Trial Design

# 4.1 Overall Design

This is an open-label, multicenter Phase 1/2a dose escalation, safety, PK and pharmacodynamic trial of BNT411 with expansion cohorts in a mixed population of patients with solid tumors. The trial consists of three parts:

- **Part 1A** will be a monotherapy dose escalation in patients with advanced solid cancers until the MTD and/or RP2D of BNT411 as monotherapy are defined.
- **Part 1B** will be a combination dose escalation in patients with chemotherapy-naïve ES-SCLC until the MTD and/or RP2D of BNT411 in combination with atezolizumab, carboplatin and etoposide are defined.
- Part 2 will consist of expansion cohorts in solid cancers based on data generated in Part 1A and Part 1B.

Part 1B is planned to start before the MTD/RP2D is reached in Part 1A using a bifurcated trial design. Bifurcation is planned to start when Part 1A monotherapy dose level 5 (2.4  $\mu$ g/kg) evaluation is completed and deemed safe. At this point, Part 1B would start with one dose level below (i.e. dose level 4 [1.2  $\mu$ g/kg]). Based on nonclinical data, this dose level is considered to be the anticipated minimally efficacious dose. Atezolizumab, carboplatin and etoposide will be administered at fixed doses approved for the indication of ES-SCLC.

In case the MTD for monotherapy is identified prior to dose level 5, the bifurcation will start one dose level below the monotherapy MTD dose level. The sponsor together with the Safety Review Committee (SRC) may explore intermediate dose levels to bifurcate from monotherapy to combination dose escalation based on safety, PK, pharmacodynamics and preliminary efficacy data generated.

The dose level of BNT411 in Part 1B at any given time will always be one dose level below that in Part 1A. This approach will allow for rapid and safe triggering of the combination dose escalation. This will lead to the timely optimization of the combination schedule that will be taken to the Phase 2 trial. At the same time, patient safety is safeguarded by generating enough monotherapy data before bifurcation, and clear rules for parallel dose escalations are outlined.

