2 out of 3 OR at least 2 out of 6	Dose escalation will be stopped, the MTD will be considered to be reached at the one before the last dose level explored. The sponsor will decide, based on a discussion between the investigators and the sponsor at a dose escalation meeting, if additional patients need to be enrolled and at which dose to finalize the trial
Any condition which would require further clarification of safety	A cohort of 6 patients can eventually be extended and more patients can be enrolled in a cohort if decided by the sponsor based on a discussion between the investigators and the sponsor at a dose escalation meeting

DLT = dose-limiting toxicity; MTD = maximal tolerated dose.

The dose escalation will potentially (dependent on data collected during the trial) evaluate BNT411 at eight main dose levels as shown in Table 4-2.

Dose Level	Dose of BNT411* (μg/kg/administration)	Dose Increment*
1**	0.05	Starting dose
2**	0.15	200%
3**	0.45	200%
4	1.2	166%
5	2.4	100%
6	4.8	100%
7	9.6	100%
8	16.0	66%

**Table 4-2:** BNT411 dose increments

Based on the nonclinical toxicology profile, which does not suggest a steep dose- or exposure-response curve and showed no severe toxicity findings, an initial dose tripling is proposed. Subsequently, standard dose doubling is proposed starting from dose level 4 in line with the FDA Guidance for Industry S9 Nonclinical Evaluation for Anticancer Pharmaceuticals. Based on nonclinical data, dose level 4 is the anticipated minimal efficacious dose. Furthermore, the sponsor proposes seven optional, intermediate dose levels at 0.075, 0.225, 0.9, 1.8, 3.6, 7.2 and  $12.8 \,\mu g/kg$ .

To be eligible for DLT assessment, patients should receive all three infusions of BNT411 during Cycle 1 (DLT assessment period). Patients who will not be able to fulfil the criteria for the DLT assessment will be replaced and this only applies to patients who do not experience a DLT. As long as patients do not experience a DLT, patients who have been replaced can continue with BNT411 treatment and follow the same trial procedures until unacceptable toxicity, documented disease progression, and/or the onset of a new anti-cancer therapy (palliative radiotherapy of, for example, painful bone metastases not defined as target lesions will be allowed).

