#### 4.1.1.3 Dose Escalation in Part 1B

The rules and details on the bifurcated design are outlined in Section 4.1.

The dose escalation in Part 1B follows the classical 3+3 design as described above in Section 4.1.1.1. However, in the case that any dose level in Part 1B is declared as MTD, dosing in Part 1B should stop. The monotherapy dose escalation in Part 1A can proceed independently of Part 1B until MTD and/or RP2D of BNT411 monotherapy are established. Refer to Section 6.6.5 for safety stopping criteria.

After 4 cycles of treatment, PCI is permitted as per local guidelines and will be reported on the electronic Case Report Form (eCRF). No systemic anti-cancer therapies should be administered concurrently with PCI. A delay of ≤21 days in administering systemic anti-cancer therapies due to PCI is not considered a protocol deviation. Thoracic radiation with curative intent or the intent to eliminate residual disease is not permitted. Palliative thoracic radiation and other palliative radiotherapies are allowed.

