## 6.6.7 Atezolizumab Dose Modification and Management of Specific Adverse Events

Dose modifications for atezolizumab are permitted according to the atezolizumab Prescribing Information valid in a given country and local standard-of-care. Management of specific adverse events should be done according to the atezolizumab Prescribing Information and local standard of care.

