#### **DLT Evaluation Set**

The DLT evaluation set includes all patients from the safety set who either have completed the DLT evaluation period and meet the minimum exposure criterion or have experienced a DLT during the DLT evaluation period (Cycle 1).

Patients who do not experience any DLT during the DLT evaluation period are considered to be evaluable if they have been observed for minimum 21 days following the first dose and are considered to have sufficient safety data to conclude that a DLT did not occur. A patient is considered to have met the minimum exposure criterion if the relative dose intensity (RDI) of BNT411 in Cycle 1 is 100%.

Patients who are excluded from the DLT evaluation set will be replaced.

The DLT evaluation set will be used for the evaluation of DLTs in order to assess the MTD and the RP2D. The safety set will be used for all other safety analyses, while the mITT set will be used for efficacy analyses (Part 2 only).

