7 ANALYSIS SETS AND SUBGROUPS

7.1 Analysis sets

Enrolled Set

Enrolled set will have the patients with a valid date of informed consent.

Safety Set

The Safety set is defined as all patients who received BNT411 (i.e., at least one dose of BNT411).

DLT Evaluation Set

The DLT evaluation set includes all patients from the Safety set who either have completed the DLT evaluation period (i.e., have been observed for minimum 21 days following the first dose) and meet the minimum exposure criterion (i.e., when the relative dose intensity [RDI] of BNT411 in Cycle 1 is 100%) or have experienced a DLT during the DLT evaluation period (Cycle 1).

Patients who do not experience any DLT during the DLT evaluation period are considered to be evaluable if they have been observed for minimum 21 days following the first dose and are considered to have sufficient safety data to conclude that a DLT did not occur.

Patients who are excluded from the DLT evaluation set will be replaced.

Pharmacokinetic (PK) Full Set

The PK Full set will consist of all patients who receive at least one dose of BNT411 and have at least one quantifiable post-dose PK sample.

Pharmacokinetic (PK) Evaluable Set

The PK Evaluable set will consist of all patients in the PK Full Set with a sufficient number of quantifiable PK samples to reliably estimate one or more PK parameters.

Pharmacodynamic (PD) Set

The PD set is defined as all patients who received IMP (i.e., at least one dose of BNT411) and have at least one valid post-dose PD assessment.

The DLT evaluation set will be used for the evaluation of DLTs in order to assess the MTD and the RP2D. The Safety set will be used for all other safety analyses. The PK Full Set, PK Evaluable Set and PD analysis set will be used for the PK and PD summaries, respectively.

Most patient data listings will be based on the Safety set. The Enrolled set will be used to summarize the patient disposition summary and some patient data listings.

For the screened patients, the summary is not by cohort, the number and percentage of patients having failed screening (reported as screen failure in the electronic Case Report Form [eCRF]) will be presented along with a summary of the primary reason for screening failure.

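### In Part 1B a DLT-free patient is evaluable on BNT411 exposure alone, so a patient who missed part of the partner regimen can count as a full no-DLT result for the combination

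*Protocol*

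**What the plan says.** Part 1B escalates until the MTD and/or "RP2D of BNT411 in combination with atezolizumab, carboplatin and etoposide are defined" (Protocol 4.1). The target is a dose of BNT411 within a four-drug regimen.

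Every statement of who is evaluable for DLTs refers to BNT411 exposure only:

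- Protocol 4.1.1.1: "To be eligible for DLT assessment, patients should receive all three infusions of BNT411 during Cycle 1 (DLT assessment period"). The synopsis says the same. Section 4.1.1.3 carries the rules over: "The dose escalation in Part 1B follows the classical 3+3 design as described above in Section 4.1.1.1".
- Protocol 9.3: "A patient is considered to have met the minimum exposure criterion if the relative dose intensity (RDI) of BNT411 in Cycle 1 is 100" percent.
- SAP 7.1: patients must have completed the DLT period and "meet the minimum exposure criterion (i.e., when the relative dose intensity [RDI] of BNT411 in Cycle 1 is 100" percent). There is no separate version for Part 1B.

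A DLT-free patient also needs at least 21 days of observation and enough safety data to conclude that no DLT occurred. A patient with a DLT in Cycle 1 is evaluable whatever the exposure. Replacement (Protocol 4.2.1) is triggered by not being DLT-evaluable or by never receiving BNT411. Both documents use this set to assess the MTD and RP2D.

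For the partner drugs, Protocol 6.6.7 states: "Dose modifications for atezolizumab are permitted according to the atezolizumab Prescribing Information valid in a given country and local standard-of-care". Sections 6.6.8 and 6.6.9 say the same for carboplatin and etoposide. None of the three excludes Cycle 1.

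**The concern.** The exposure rule is strict for one drug and silent for three. A DLT-free patient short of BNT411 in Cycle 1 leaves the set and is replaced. A DLT-free patient with three full BNT411 infusions but reduced or missed atezolizumab, carboplatin or etoposide stays in and counts as tolerating the combination.

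Escalation rests on three to six evaluable patients per cohort, so each no-DLT result carries weight. If partial exposure to the partners lowers DLT risk, such a patient pulls the observed combination DLT rate down and makes escalation more likely. The hazard that could be understated is the added or potentiated toxicity of the combination, which Protocol 2.3.2 says cannot be ruled out.

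The omission may also be informative. Etoposide follows BNT411 on Day 2 and is given again on Day 3. A Day 2 reaction that falls short of a DLT could lead to a skipped etoposide dose while BNT411 continues on Days 8 and 15.

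**Working it through.** The plan states no figure to reproduce: there is no hypothesis test, and neither document gives a DLT rate. The check has two parts.

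**1. Does the rule admit such a patient?** SAP 8.5.1 defines treatment duration as (last date − first date + planned duration)/7. For the third dose of a Part 1B cycle the planned duration is 8 days. With BNT411 on Days 2, 8 and 15:

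- Actual duration = (15 − 2 + 8)/7 = 3.0 weeks, equal to planned.
- Actual cumulative BNT411 dose = planned.
- RDI = 100%, because no partner-drug quantity enters the BNT411 formula.

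The observation and safety-data conditions do not refer to partner drugs. Protocol 6.6.3.2 says patients must complete the DLT period before modification criteria apply, but that covers only the criteria in that section, which concern BNT411. So the patient is admitted.

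**2. How much could one such patient matter?** From Table 4-1, a cohort passes with 0 DLTs in 3, or 1 in 3 followed by none in the next 3:

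P(pass) = P(0 of first 3) + P(1 of first 3) × P(0 of next 3).

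Assume DLT risk p = 0.33 on the full regimen. With everyone fully exposed:

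- P(0 of 3) = 0.67³ = 0.3008
- P(1 of 3) = 3 × 0.33 × 0.67² = 0.4444
- P(pass) = 0.3008 + 0.4444 × 0.3008 = 0.434

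Now give one patient risk q.

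- In the first three: P(0) = (1 − q) × 0.67² and P(1) = q × 0.67² + (1 − q) × 2 × 0.33 × 0.67. The next three are unchanged.
- In the second three: the first three are unchanged, and P(0 of next 3) = (1 − q) × 0.67².
- Average over the six positions, which weights the two cases equally.

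| q (assumed) | In first three | In second three | Average | Change from 0.434 |
|---|---|---|---|---|
| 0.30 | 0.448 | 0.440 | 0.444 | +1.0 point |
| 0.28 | 0.457 | 0.444 | 0.451 | +1.6 points |
| 0.15 | 0.515 | 0.470 | 0.493 | +5.8 points |

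At assumed risks of 40% and 20% the pass probability goes from 0.309 to 0.363, or +5.4 points.

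These figures are conditional on one affected patient being present. If instead each patient has an assumed 5% chance of being affected, with 33% and 15%, the average risk is 0.95 × 0.33 + 0.05 × 0.15 = 0.321. Then P(pass) = 0.679³ + 3 × 0.321 × 0.679² × 0.679³ = 0.452, or +1.8 points.

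**The case against.** The case against giving this much weight is strong on likelihood and size.

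- **Timing and eligibility.** Atezolizumab and carboplatin are given on Day 1, before the first BNT411 dose on Day 2 (Protocol 6.1.1). Patients with a contraindication to a partner drug are excluded, and adequate organ function is required. Protocol 4.1 plans fixed approved partner doses. The plausible residue is a missed Day 2 or Day 3 etoposide dose.
- **DLT definition.** Grade 3 or 4 neutropenia, leucopenia, anemia and thrombocytopenia due solely to chemotherapy are not DLTs in Part 1B (6.6.2). Less chemotherapy would therefore remove few countable events, which favours the smaller contrasts in the table. The investigator and sponsor may also judge other toxicities to be DLTs.
- **Oversight.** The Safety Review Committee sees all relevant data for each cohort, cohorts can be extended, the RP2D is an integrated judgement, and Part 1B stays one dose level below Part 1A.
- **Consequence.** SAP Section 3 says Part 2 no longer applies, so no expansion cohort in this trial will be treated at a Part 1B RP2D.
- **Principle.** BNT411 is the only drug escalated, so tying minimum exposure to it is understandable.

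All of this stands as a limit on size. None of it alters the evaluability definition or the replacement rule. Committee review could catch such a patient, but only by discretion, since Table 4-1 counts evaluable patients as defined.

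A reader might infer that the combination MTD is unreliable, or that every under-exposed patient adds 5 points or more to the pass probability. The documents support neither. They do not show that any such patient exists, and effects of that size require DLT risk to halve or more when a partner drug is missed.

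**Conclusion.** The point holds in a limited form. In Part 1B the stated rule lets a DLT-free patient with incomplete partner-drug exposure count as a full no-DLT result. If partial exposure lowers risk, the bias runs towards a lower combination DLT rate and easier escalation. Patients with a DLT are unaffected.

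The size cannot be fixed from the documents. With 33% assumed on the full regimen and one affected patient in the cohort, the rise in pass probability is about 1, 2 or 6 points for an assumed risk in that patient of 30%, 28% or 15%. The lower part of that range is easier to defend, given the DLT exclusions for chemotherapy-related cytopenias. This is a worthwhile, inexpensive improvement, and it does not by itself invalidate the Part 1B dose finding.

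**What to change.** For Part 1B, in Protocol 9.3 and SAP 7.1:

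1. Require a minimum Cycle 1 exposure to each of atezolizumab, carboplatin and etoposide for a DLT-free patient to be evaluable. The sponsor sets the minimum.
2. Keep every patient with a DLT evaluable, as now.
3. Refer a DLT-free patient whose partner drug was withheld or reduced for toxicity to the Safety Review Committee instead of replacing that patient automatically. Automatic removal would discard informative cases.

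The SAP lists Part 1B cohorts at 1.2 and 2.4 µg/kg, and these may already be complete. For completed cohorts, leave the set as it is and report Part 1B DLT counts with and without DLT-free patients below the minimum. SAP 8.5.1 already derives Cycle 1 exposure per drug for the DLT evaluation set, so no new data are needed.

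The cost is a short addition to each document and an occasional replacement patient for open cohorts, or one extra table for completed ones. No treatment rule changes.

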# 9.4 Statistical Analyses

Statistical analyses will be performed by the BioNTech or a designated CRO. All statistical analyses will be carried out using SAS®, Version 9.4 or higher, and/or other statistical software as required.

The statistical analysis plan will be finalized prior to database snapshot for the main statistical analysis, it will include a more technical, and detailed description of the statistical analyses described in this section. This section is a summary of the planned statistical analyses of the most important endpoints including primary and key secondary endpoints.

#### 9.4.1 General Considerations

Continuous variables will be summarized by cohort using the following descriptive statistics: number of patients (n), mean, standard deviation, median, minimum and maximum.

Categorical variables will be summarized by cohort presenting absolute and relative frequencies (n and %) of patients in each category.

Time-to-event-endpoints (DOR, PFS and OS) will be analyzed using Kaplan-Meier methodology by cohort and censored in accordance with the FDA Guidance: "Clinical Trial Endpoints for the Approval of Cancer Drugs and Biologics" and the EMA guidance "Guideline on the evaluation of anti-cancer medicinal products in man". Censoring rules will be defined in the SAP.

The median survival time (including 95% confidence limits according to Brookmeyer and Crowley) and the first and third quartile will be presented. Survival rates (including 95% confidence interval based on Greenwood's formula) as well as the number and percentage of patients with events, censored and under risk will be displayed for selected time points (e.g. at 3, 6, 12 months). The time-to-event analysis will be illustrated using Kaplan-Meier plots.

Baseline is defined as last available value prior to first dose of trial treatment (i.e. BNT411, or atezolizumab, carboplatin, and etoposide).

#### 9.4.2 Primary Endpoint(s)

The primary objective of the trial is to assess the safety profile of the regimen based on the following endpoints:

- Occurrence of dose limiting toxicities (DLTs) within a patient during the DLT evaluation period
- Occurrence of treatment-emergent adverse events (TEAE) within a patient including grade ≥3, serious, fatal TEAE by relationship
- Occurrence of dose reduction and discontinuation of BNT411 within a patient due to treatment-emergent adverse events (TEAE)

And to determine the MTD and/or RP2D defined as follows:

- MTD the highest tolerated dose
- RP2D based on integrated evaluation of safety, tolerability, clinical benefit, PK, and pharmacodynamics data, for all dose levels tested.

A treatment emergent AE is defined as any AE with an onset date on or after the first administration of trial treatment (if the AE was absent before the first administration of trial treatment) or worsened after the first administration of trial treatment (if the AE was present before the first administration of trial treatment). AEs with an onset date more than 60 days after the last administration of trial treatment will be considered as treatment emergent only if assessed as related to trial treatment by the investigator. Treatment-emergent AEs will be summarized overall and by treatment arm. The trial treatment includes BNT411, atezolizumab, carboplatin, and etoposide.

AEs will be coded using the most recent version of Medical Dictionary for Regulatory Activities (MedDRA®) coding system to get a System Organ Class (SOC) and Preferred Term (PT) for each AE and graded for severity using NCI CTCAE v5.0.

The number and percentage of patients reporting at least one AE will be summarized by PT nested within SOC for each of the following AE types:

- any AE
- related AE
- Grade >3 AE
- related Grade ≥3 AE
- any SAE
- related SAE
- SAE leading to death
- AE leading to dose reduction
- AE leading to permanent discontinuation of treatment
- DLT.

Moreover, the number and percentage of patients with any AE will be summarized by worst NCI CTCAE grade by PT nested within SOC.

DLTs will be presented in terms of listings presenting the reported term and MedDRA PT and SOC term, its time of onset, duration, and outcome, relationship, NCI CTCAE grade, and seriousness including dose exposure data.

